**Table 5.3: Summary of Statistical analyses for immunogenicity analysis of secondary endpoints**

Endpoint	Visit and Group	Description
Serotype specific pneumococcal OPA titer for each of the 21 serotypes	V01 and V02 - Toddlers V04, V05 and V06 - Infants OPA subset	OPA GMT and 95% CI, corresponding Forest Plot
	V02/V01 - Toddlers V06/V05 - Infants OPA subset	OPA GM ratio (post/pre) and 95% CI
	V01 and V02 - Toddlers V04, V05 and V06 - Infants OPA subset	Proportion of participants with titer $\geq$ LLOQ and 95% CI
	V02 - Toddlers V04 and V06 - Infants OPA subset	OPA GMT ratio and 95% CI between any SP0202 group and Prevnar 13 (ie, Group 1/Group 4, Group 2/Group 4, Group 3/ Group 4; Group 5/Group 8, Group 6/Group 8, Group 7/Group 8) and corresponding Forest Plot
	V04 and V06 - Infants OPA subset	OPA GMT ratio and 95% CI between SP0202 groups (ie, Group 6/Group 5, Group 7/Group 5 and Group 7/Group

\* Not applicable from protocol Version 5.0

† Immunogenicity to ENGERIX-B will be presented according to the number of doses received

		6), and corresponding Forest Plot
	V01 and V02 - Toddlers V04, V05 and V06 - Infants OPA subset	OPA titer RCDC
Anti-tetanus and anti-diphtheria	V01 and V02 - Toddlers V01* and V04 - Infants	GMC and 95% CI
		RCDC
		Proportion of participants with concentration $\geq 0.10$ IU/mL and 95% CI
	V01* and V04 - Infants	Proportion of participants with concentration $\geq 1.0$ IU/mL and 95% CI
Anti-PT, anti-FHA, anti-PRN and anti-FIM	V01 and V02 - Toddlers	GMC and 95% CI
	V01* and V04 - Infants	RCDC
	V02/V01 - Toddlers	Proportion of participants with pertussis vaccine response from pre to post vaccination and 95% CI
Anti-PRP	V01 and V02 - Toddlers V04 - Infants	GMC and 95% CI
		Proportion of participants with concentration $\geq 0.15$ $\mu$ g/mL and 95% CI
		Proportion of participants with concentration $\geq 1.0$ $\mu$ g/mL and 95% CI
		RCDC
Anti-Hepatitis B	V04 - Infants	GMC and 95% CI
		RCDC
		Proportion of participants with concentration $\geq 10$ IU/mL and 95% CI
		Proportion of participants with concentration $\geq 100$ IU/mL and 95% CI
Anti-Rotavirus	V01*, V04 - Infants	GMC and 95% CI
		RCDC
Anti-measles	V06 - Infants	GMC and 95% CI
		RCDC
		Proportion of participants with concentration $\geq 255$ mIU/mL and 95% CI
Anti-mumps	V06 - Infants	GMC and 95% CI
		RCDC
		Proportion of participants with concentration $\geq 10$ mumps Ab U/mL and 95% CI

Anti-rubella	V06 - Infants	GMC and 95% CI
		RCDC
		Proportion of participants with concentration $\geq$ 10 IU/mL and 95% CI
Anti-varicella	V06 - Infants	GMC and 95% CI
		RCDC
		Proportion of participants with concentration $\geq$ 5 glycoprotein units/mL and 95% CI

\* Not applicable from protocol Version 5.0

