	
One month after 6 MoA vaccination (D150) in all subjects:
 
 • IgG Abs against hepatitis B surface antigen concentration ≥ 10 mIU/mL and ≥ 100 mIU/mL • Anti-PRP Ab concentrations • Anti-PRP Ab concentrations ≥ 0.15 μg/mL and ≥ 1.0 μg/mL • Anti-poliovirus (types 1, 2, and 3) Ab titers • Anti-rotavirus serum IgA Ab concentrations • Anti-rotavirus serum IgA Ab concentrations with ≥ 3-fold rise over baseline* • Anti-pertussis (PT, FHA, PRN, and FIM) Ab concentrations • Anti-diphtheria toxoid Ab concentrations • Anti-diphtheria toxoid Ab concentrations ≥ 0.01 IU/mL and ≥ 0.1 IU/mL • Anti-tetanus toxoid Ab concentrations • Anti-tetanus toxoid Ab concentrations ≥ 0.01 IU/mL and ≥ 0.1 IU/mL 
* Not applicable from protocol Version 5.0
 
One month after 12-15 MoA vaccination (D330-D420) in all subjects:
 
 • Anti-measles Ab concentrations • Anti-measles Ab concentrations ≥ 255 mIU/mL • Anti-mumps Ab concentrations • Anti-mumps Ab concentrations ≥ 10 mumps Ab U/mL • Anti-rubella Ab concentrations • Anti-rubella Ab concentrations ≥ 10 IU/mL • Anti-varicella Ab concentrations • Anti-varicella Ab concentrations ≥ 5 glycoprotein enzyme-linked immunosorbent assay (gpELISA) units/mL 																														

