- Pre-vaccination ≥ 4 times the LLOQ, then post-vaccination should achieve a 2-fold response (post-vaccination/pre-vaccination ≥ 2)

- Anti-diphtheria toxoid Ab concentrations
- Anti-diphtheria toxoid Ab concentrations $\geq 0.1 \text{ IU/mL}$ and $\geq 1.0 \text{ IU/mL}$
- Anti-tetanus toxoid Ab concentrations
- Anti-tetanus toxoid Ab concentrations $\geq 0.1 \text{ IU/mL}$ and $\geq 1.0 \text{ IU/mL}$

Infants

Before first vaccination in all subjects (D0)^a:

- Anti-rotavirus serum immunoglobulin (Ig) A Ab concentrations
- Anti-pertussis (PT, FHA, PRN, and FIM) Ab concentrations
- Anti-diphtheria toxoid Ab concentrations
- Anti-tetanus toxoid Ab concentrations

One month after 6 MoA vaccination (D150) in all subjects:

- IgG Abs against hepatitis B surface antigen concentration $\geq 10 \text{ mIU/mL}$ and $\geq 100 \text{ mIU/mL}$
- Anti-PRP Ab concentrations
- Anti-PRP Ab concentrations $\geq 0.15 \mu\text{g/mL}$ and $\geq 1.0 \mu\text{g/mL}$
- Anti-poliovirus (types 1, 2, and 3) Ab titers
- Anti-rotavirus serum IgA Ab concentrations
- Anti-rotavirus serum IgA Ab concentrations with ≥ 3 -fold rise over baseline^a
- Anti-pertussis (PT, FHA, PRN, and FIM) Ab concentrations
- Anti-diphtheria toxoid Ab concentrations
- Anti-diphtheria toxoid Ab concentrations $\geq 0.01 \text{ IU/mL}$ and $\geq 0.1 \text{ IU/mL}$
- Anti-tetanus toxoid Ab concentrations
- Anti-tetanus toxoid Ab concentrations $\geq 0.01 \text{ IU/mL}$ and $\geq 0.1 \text{ IU/mL}$

^a Not applicable from protocol Version 5.0

One month after 12-15 MoA vaccination (D330-D420) in all subjects:

- Anti-measles Ab concentrations
- Anti-measles Ab concentrations \geq 255 mIU/mL
- Anti-mumps Ab concentrations
- Anti-mumps Ab concentrations \geq 10 mumps Ab U/mL
- Anti-rubella Ab concentrations
- Anti-rubella Ab concentrations \geq 10 IU/mL
- Anti-varicella Ab concentrations
- Anti-varicella Ab concentrations \geq 5 glycoprotein enzyme-linked immunosorbent assay (gpELISA) units/mL

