## List of Abbreviations

Ab	antibody
AE	adverse event
AESI	adverse event of special interest
AR	adverse reaction
BL	blood sample
CI	confidence interval
CRB	(electronic) case report book [all the case report forms for a participant]
CSR	clinical study report
D	day
DC	diary card
DMC	Data Monitoring Committee
dil	dilution
DTaP	diphtheria, tetanus, and acellular pertussis
ECL	electro-chemiluminescence assay
ELISA	enzyme linked immunosorbent assay
ESDR	early safety data review
EU	endotoxin units
FAS	full analysis set
FHA	filamentous hemagglutinin
FIM	fimbriae types 2 and 3
GM	geometric mean
GMC	geometric mean concentration
GMCR	geometric mean concentration ratio
GMT	geometric mean titer
GMTR	Geometric mean titer ratio
HB	hepatitis B
Hib	Haemophilus influenza b
IgA	immunoglobulin type A
IgG	immunoglobulin type G
IU	international unit
IRT	interactive response technology
LLOQ	lower limit of quantification
MedDRA	Medical Dictionary for Regulatory Activities
mIU	milli-international units
MOPA	Multiplexed opsonophagocytic killing assay

---

M-M-R	measles, mumps, rubella
NA	Not applicable
OPA	opsonophagocytic activity
PC	phone call
PCV	pneumococcal conjugate vaccine
PPAS	per-protocol analysis set
PD3	1-month post-dose 3
PD4	1-month post-dose 4
PRN	pertactin
PRP	polyribosyl-ribitol phosphate
PT	pertussis toxoid / toxin
PT	preferred term
Q1; Q2; Q3	first quartile; second quartile (median); third quartile
RCDC	reverse cumulative distribution curve
SAE	serious adverse event
SafAS	safety analysis set
SAP	statistical analysis plan
SD	standard deviation
SMT	Safety Management Team
SOC	system organ class (primary)
TLF	table(s), listing(s), and figure(s)
ULOQ	upper limit of quantification
Vac	vaccination
WHO	World Health Organization

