#### One month after 6 MoA vaccination (D150) in all participants:

- IgG Abs against hepatitis B surface antigen concentration  $\geq 10$  mIU/mL and  $\geq 100$  mIU/mL
- Anti-PRP Ab concentrations
- Anti-PRP Ab concentrations  $\geq 0.15$   $\mu$ g/mL and  $\geq 1.0$   $\mu$ g/mL
- Anti-poliovirus (types 1, 2, and 3) Ab titers
- Anti-rotavirus serum IgA Ab concentrations
- Anti-rotavirus serum IgA Ab concentrations with  $\geq 3$ -fold rise over baseline\*
- Anti-pertussis (PT, FHA, PRN, and FIM) Ab concentrations
- Anti-diphtheria toxoid Ab concentrations
- Anti-diphtheria toxoid Ab concentrations  $\geq 0.01$  IU/mL and  $\geq 0.1$  IU/mL
- Anti-tetanus toxoid Ab concentrations
- Anti-tetanus toxoid Ab concentrations  $\geq 0.01$  IU/mL and  $\geq 0.1$  IU/mL

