#### 4.3.2.2 Thresholds

Generally, if the computed value is  $\geq x$ , then the derived indicator will be “Yes” for that test, otherwise indicator will be "No". Note: If the computed value is missing, indicator will be missing. The thresholds are summarized in the tables below:

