**Table 4.6: Immunogenicity Thresholds of interest for Stage 2/ Infants**

Endpoints	Baseline (V01)*	30 days post- Dose 3 (V04)	Before Dose 4 (V05)	30 days post- Dose 4 (V06)
Pneumococcal serotype specific binding IgG	$\geq 0.35 \mu\text{g/mL}$	$\geq 0.35 \mu\text{g/mL}$	$\geq 0.35 \mu\text{g/mL}$	$\geq 0.35 \mu\text{g/mL}$
Pneumococcal serotype specific functional Ab (OPA)		$\geq \text{LLOQ (1/dil)}$	$\geq \text{LLOQ (1/dil)}$	$\geq \text{LLOQ (1/dil)}$
Anti-diphtheria and anti- tetanus Ab	$\geq 0.01 \text{ IU/mL}$ , $\geq 0.1 \text{ IU/ mL}$ , $\geq 1.0 \text{ IU/mL}$	$\geq 0.01 \text{ IU/mL}$ , $\geq 0.1 \text{ IU/ mL}$ , $\geq 1.0 \text{ IU/mL}$		
Anti-poliovirus 1, 2, and 3 Ab	-	$\geq 8 \text{ (1/dil)}$		
Anti-PRP Ab	-	$\geq 0.15 \mu\text{g/mL}$ $\geq 1.0 \mu\text{g/mL}$		
Anti-hepatitis B Ab	-	$\geq 10 \text{ mIU/mL}$ $\geq 100 \text{ mIU/mL}$		
Anti-measles Ab			-	$\geq 255 \text{ mIU/mL}$
Anti-mumps Ab			-	$\geq 10 \text{ mumps Ab U/mL}$
Anti-rubella Ab			-	$\geq 10 \text{ IU/mL}$
Anti-varicella Ab			-	$\geq 5 \text{ glycoprotein units/mL}$

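### SAP Table 5.3 states the infant hepatitis B cut-offs in IU/mL instead of mIU/mL, a factor of 1000; SAP 5.7 also misdates the added infant polio endpoint

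*SAP*

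**What the plan says.** The hepatitis B secondary endpoint for infants is the proportion above two antibody cut-offs, measured about D150 (V04), one month after the 6-month vaccination. The protocol synopsis defines it as "IgG Abs against hepatitis B surface antigen concentration ≥ 10 mIU/mL and ≥ 100 mIU/mL". Protocol 9.2.2.1.2 repeats those values, and SAP 4.2.2.2 lists the same endpoint: "IgG Abs against hepatitis B surface antigen concentration $\geq 10$ mIU/mL and $\geq 100$ mIU/mL". The V04 column of SAP Table 4.6, which feeds the derivation of the threshold indicators, also gives 10 and 100 mIU/mL.

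SAP Table 5.3, which lists the statistics to be produced for the secondary immunogenicity endpoints, has two anti-hepatitis B proportion rows at V04. Both are in IU/mL: one at 10 IU/mL, the other "Proportion of participants with concentration $\geq 100$ IU/mL and 95% CI".

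SAP 5.7, on changes to the planned analyses, has a single entry. It says that a polio threshold of 1:8 was added for Stage 2 infants after Dose 4. It does not mention hepatitis B.

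**The concern.** One SAP gives two sets of cut-offs for the same named endpoint at the same visit, and they differ only in the unit prefix. Table 5.3 is where a programmer or table author would look to see which secondary proportions to produce and how to title them. If the IU/mL rows were followed, the reported proportions would describe a far higher antibody level than the protocol's endpoint. If only the titles were taken from Table 5.3, correct proportions would carry a wrong label. SAP 5.1.2.2.2 also plans to analyse hepatitis B antibody levels by number of doses received, so the error could carry into each of those displays.

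The polio entry is a separate and smaller matter. It names a time point at which no infant polio titer is planned.

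**Working it through.** **1. Hepatitis B cut-offs side by side** (infants, V04 / D150; the repeated synopsis page is counted once)

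| Place | Cut-offs as written | In mIU/mL |
|---|---|---|
| Protocol synopsis, secondary endpoints | 10 and 100 mIU/mL | 10 and 100 |
| Protocol 9.2.2.1.2 | 10 and 100 mIU/mL | 10 and 100 |
| SAP 4.2.2.2 | 10 and 100 mIU/mL | 10 and 100 |
| SAP Table 4.6 | 10 and 100 mIU/mL | 10 and 100 |
| SAP Table 5.3 | 10 and 100 IU/mL | 10,000 and 100,000 |

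Four statements agree and one does not.

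**2. Size.** The SAP's abbreviation list expands mIU as "milli-international units", so 1 IU = 1000 mIU.

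- Lower cut-off: 10 IU/mL × 1000 = 10,000 mIU/mL; 10,000 / 10 = 1000.
- Upper cut-off: 100 IU/mL × 1000 = 100,000 mIU/mL; 100,000 / 100 = 1000.
- The lower Table 5.3 cut-off against the upper protocol cut-off: 10,000 / 100 = 100.

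The two sets of cut-offs therefore do not overlap.

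**3. Could the Table 5.3 unit be intended, or lost in text extraction?**

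- A lost prefix is unlikely. Both hepatitis B rows lack it, while the measles row of the same table keeps it: "Proportion of participants with concentration $\geq 255$ mIU/mL and 95% CI".
- It is not a table-wide unit convention, for the same reason. The rubella row at 10 IU/mL agrees with the protocol and should stay.
- It is not a recorded change. SAP 5.7 lists only the polio addition.

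**4. What the factor could do to a reported proportion.** The documents give no hepatitis B distribution, so this is an illustration on assumed values only: log-normal concentrations, geometric mean (GMC) of 100, 1000 or 5000 mIU/mL, SD of log10 of 0.4 or 0.7. The proportion at or above a cut-off c is 1 − Φ((log10 c − log10 GMC) / SD). For example, with GMC 1000 and SD 0.7:

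- at 10 mIU/mL: 1 − Φ((1 − 3) / 0.7) = 99.8%
- at 10 IU/mL: 1 − Φ((4 − 3) / 0.7) = 7.7%

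Over the whole grid:

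| Cut-off | Read as mIU/mL | Read as IU/mL |
|---|---|---|
| 10 | 92% to 100% | 0% to 33% |
| 100 | 50% to 100% | 0% to 3% |

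The finding does not depend on these figures.

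**5. Polio time point.**

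- Protocol Table 9.4 and 9.2.2.2, and SAP Table 4.4 and 4.2.2.3, place the infant polio assay on BL0002 only. That sample is drawn at V04, after Dose 3.
- SAP Table 4.6 puts the threshold of 8 (1/dil) in the V04 column only.
- The post-Dose 4 sample, BL0004 at V06, has no polio test.
- SAP 3.2 gives infants Pentacel at 2, 4 and 6 months, with its fourth dose after the last study visit.

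The plan therefore yields no post-Dose 4 polio titer for the SAP 5.7 entry to refer to.

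**The case against.** The strongest reply is that the governing rule is already right. SAP 4.3.2.2 sets out how threshold indicators are derived and says "The thresholds are summarized in the tables below"; Table 4.6 then gives mIU/mL. Table 5.3 is only a summary, and an incomplete one: it has no polio row, no 0.01 IU/mL row for diphtheria and tetanus, and no rotavirus fold-rise row. A programmer would have to return to section 4 in any case. The hepatitis B GMC and distribution-curve rows carry no cut-off and are unaffected. No hypothesis is tested, and no primary endpoint, analysis set or sample size is touched. On polio, the SAP 5.7 entry specifies no analysis and misleads nobody about sampling.

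Most of this stands, and it limits the consequence. It does not remove the contradiction. Table 5.3 states an analysis threshold in the SAP's list of statistics to be produced, and a reader who follows those rows gets the wrong endpoint. That the correct value appears elsewhere makes the repair easy but does not make the row right. The polio point would not merit raising alone and is kept only as a correction to the record.

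**Conclusion.** The concern holds. Both hepatitis B proportion rows of SAP Table 5.3 are wrong as written, by a factor of exactly 1000. This rests on the SAP's own expansion of mIU and on taking the protocol and the other two SAP statements as the intended endpoint. The effect is confined to descriptive secondary outputs programmed or labelled from that table; how many outputs or infants would be affected cannot be told from the documents. The post-Dose 4 label in SAP 5.7 is also wrong, with no analytic effect. Both should be corrected.

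**What to change.** In SAP Table 5.3, change the two anti-hepatitis B rows to ≥10 mIU/mL and ≥100 mIU/mL, and leave the rubella row in IU/mL. In SAP 5.7, change the time point of the added infant polio endpoint from post-Dose 4 to post-Dose 3 (V04).

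The cost is two unit labels and one time-point label, with no new samples, assays or analyses. While the text is open, the authors could also add the infant polio threshold to SAP 4.2.2.2 and give polio a row in Table 5.3, since the added endpoint's visit is at present correctly stated only in Table 4.6. The unit correction does not depend on that.

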### 5.1.3 Complementary analyses

#### ***COVID-19***

Impact of COVID-19 pandemic on study conduct and disposition of participants impacted by COVID-19 pandemic situation will be summarized in tables on all participants and listed in Appendix 16 of the CSR.

If more than 20% for Stage I (Toddlers)/10% for Stage II (Infants) of randomized participants are impacted by COVID-19, and still evaluable for immunogenicity/safety at primary timepoints, additional analyses in impacted/non-impacted participants will be done on main immunogenicity and safety endpoints.

#### ***Subgroup Immunogenicity analyses***

For Infant participants, exploratory analyses will be done according to Gender (two categories: Male, Female) and Race (two categories: the modality(ies) the most represented versus the pool of the other modalities) on the main parameters:

- Percentage of participants with a PD3 serotype specific IgG concentrations  $\geq$  0.35  $\mu$ g/mL
- GM of serotype specific IgG concentrations (PD3, pre-dose 4, PD4)
- GM of serotype specific ratio concentrations (PD4/pre-dose 4)

#### ***Correlation heatmap Immunogenicity analyses***

Correlation heatmaps will be plotted for both serotype specific IgG concentrations and serotype specific OPA titers at post-vaccination for Stage I (Toddlers) and at post-dose 3 and post-dose 4 for Stage II (Infants) using the Spearman's correlation matrix across serotypes. One figure for each group separately will be plotted, and one figure pooling the three SP0202 groups will be plotted as well.

#### ***Stage 2 participants with blood sample at V01***

Participants enrolled prior to implementation of protocol Version 5.0 were to have blood sample at V01 (pre-dose 1 BL).

Main immunogenicity analysis after primary series on pneumococcal serotype specific IgG concentrations, will be performed on participants with blood sample at V01.

The subgroup and correlation analyses will be conducted in the FAS (FAS1, FAS2 or FAS3) and provided in Appendix 15 of the CSR.

## 5.2 Analysis Sets

Three analysis sets will be used: The Per-Protocol Analysis Set, the Full Analysis Set, and the Safety Analysis Set.

### 5.2.1 Per-Protocol Analysis Set

The per-protocol analysis set (PPAS) is a subset of the FAS. Three PPAS will be defined: one for Toddlers (PPAS1), one for Infants at Primary series (PPAS2) and one for Infants at Booster (PPAS3).

The participants presenting with at least one of the following relevant protocol deviations will be excluded from the PPAS1-Toddlers:

- Participant did not meet all protocol-specified inclusion criteria or met at least one of the protocol-specified exclusion criteria
- Participant did not receive vaccine
- Participant received a vaccine other than the one that he / she was randomized to receive
- Preparation and / or administration of vaccine was not done as per-protocol
- Participant did not provide the post-dose serology sample V02 in the proper time window or a post-dose serology sample was not drawn
- Participant received a protocol-prohibited medication or vaccine (identified among category 2 and 3 of concomitant medications)

In addition to the reasons listed above, participants will also be excluded from the PPAS1 if their V02 serology sample did not produce a valid serotype specific IgG test result (ie, results for all serotypes are missing).

The participants presenting with at least one of the following relevant protocol deviations will be excluded from the PPAS2 Infants Primary series:

- Participant did not meet all protocol-specified inclusion criteria or met at least one of the protocol-specified exclusion criteria\*
- Participant did not complete the vaccination schedule up to V03
- Participant received a vaccine schedule other than the one that he / she was randomized to receive

---

\* The inclusion criteria number 8 “Infants who received the first dose of hepatitis B vaccine at least 28 days before the first study visit (applicable only to infants from the US)” was applicable only before protocol amendment V5.0

- Preparation and / or administration of vaccine was not done as per-protocol
- Participant did not receive vaccine in the proper time window
- Participant did not provide the post-dose serology sample V04 in the proper time window or a post-dose serology sample was not drawn
- Participant received a protocol-prohibited medication or vaccine (identified among category 2 and 3 of concomitant medications) up to V04

In addition to the reasons listed above, participants will also be excluded from the PPAS2 if their V04 serology sample did not produce a valid serotype specific IgG test result (ie, results for all serotypes are missing).

The participants presenting with at least one of the following relevant protocol deviations will be excluded from the PPAS3-Infants Booster dose:

- Participant did not meet all protocol-specified inclusion criteria or met at least one of the protocol-specified exclusion criteria\*
- Participant did not complete the vaccination schedule up to V05
- Participant received a schedule other than the one that he / she was randomized to receive
- Preparation and / or administration of vaccine was not done as per-protocol
- Participant did not receive booster vaccine in the proper time window, ie, at 12-15 months of age and at least at V03 +180 days ( $\pm 14$ )
- Participant did not provide the post-dose serology sample V06 in the proper time window or a post-dose serology sample was not drawn
- Participant received a protocol-prohibited medication or vaccine (identified among category 2 and 3 of concomitant medications) during the booster phase

In addition to the reasons listed above, participants will also be excluded from the PPAS3 if their V06 serology sample did not produce a valid serotype specific IgG test result (ie, results for all serotypes are missing).

In the event of a local or national immunization program with a pandemic influenza vaccine or a COVID-19 vaccine, participants who receive pandemic influenza vaccine or COVID-19 vaccine at any time during the study will not be withdrawn from the study.

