5.2.7 Contraindications for Subsequent Vaccinations

5.2.7.1 Temporary Contraindications

Toddlers

Not applicable.

Infants

Should an infant experiences one of the conditions listed below, the Investigator will postpone further vaccination until the condition is resolved. Postponement must still be within the timeframe for vaccination indicated in the Table of Study Procedures.

- 1) Febrile illness (temperature $\geq 38.0^{\circ}\text{C}$ [$\geq 100.4^{\circ}\text{F}$]) or moderate or severe acute illness / infection on the day of vaccination, according to Investigator judgment
- 2) Receipt of any vaccine (other than the study vaccine[s]) in the 4 weeks preceding the study vaccination or planned receipt of any vaccine from enrollment through the last study Visit in

which SP0202 or Prevnar 13 is injected (V05), except for influenza vaccination or COVID-19 vaccination, which may be received at least 2 weeks before or 2 weeks after any study vaccination. This exception includes monovalent pandemic influenza vaccines and multivalent influenza vaccines, and COVID-19 vaccines, as applicable per local recommendation.

- 3) Long-term systemic corticosteroid therapy (prednisone or equivalent for more than 2 consecutive weeks within the past 3 months preceding the study vaccination)

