- Subject did not complete the vaccination schedule
- Subject received a schedule other than the one that he / she was randomized to receive
- Preparation and / or administration of vaccine was not done as per-protocol
- Subject did not receive booster vaccine in the proper time window, ie, at 12-15 months of age and at least at V03 +180 days (± 14)
- Subject did not provide the post-dose serology sample V06 in the proper time window or a post-dose serology sample was not drawn
- Subject received a protocol-prohibited medication or vaccine (identified among category 2 and 3, see [Section 6.7](#))

In addition to the reasons listed above, subjects will also be excluded from the PPAS3 if their V06 serology sample did not produce a valid serotype specific IgG test result (ie, results for all serotypes are missing).

The list can be completed at the time of SAP writing and before database lock.

In the event of a local or national immunization program with a pandemic influenza vaccine or a COVID-19 vaccine, subjects who receive pandemic influenza vaccine or COVID-19 vaccine at any time during the study will not be withdrawn from the study.

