#### **4.3.4.2 Duration of the Study**

The duration will be computed in days as follows: Latest period date - earliest period date + 1.

For Infants, primary series duration will be calculated as follows:

[Date of latest Visit 04 - date of earliest Visit 01] + 1

And booster phase duration will be calculated as follows:

[Date of latest Visit 06 - date of earliest Visit 05] + 1

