#### **4.3.4.3 Participant Duration**

The duration of a participant participation in the study will be computed as follows:

Maximum (Visit dates, Termination date, Follow-up date, Last contact date) - V01 date + 1.

For infant's primary series, the duration of participant participation will be computed as follows:

[Maximum (Visit dates (Visit 01 up to Visit 04), Termination date (if prematurely withdrawn before the 3rd vaccination), Last contact date (if prematurely withdrawn after the 3rd vaccination and before the 4th vaccination)) - Visit 01 date] + 1.

For the booster phase, the duration of participant participation will be computed as follows:

[Maximum (Visit dates (Visit 05 up to Visit 06), Termination date (if prematurely withdrawn post 4th vaccination), Last contact date)) - Visit 05 date] + 1.

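### The per-protocol sets omit the COVID-19 vaccine removal in protocol 5.2.9, and the SAP puts undeclared time limits on the category 2/3 exclusion

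*SAP*

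**What the plan says.** **COVID-19 vaccine.** Protocol 5.2.9 describes two situations: a COVID-19 vaccine received while solicited reactions to a study vaccine are being collected, and one received between a study dose and the blood collection. In either case it recommends that the subject leave the per-protocol population but continue in the study within the full analysis set (FAS). Section 5.2.9 calls a 2-week interval from any study dose desirable where possible. For infants, exclusion criterion 21 (protocol 5.2.5) permits COVID-19 vaccination at least 2 weeks before or 2 weeks after a study vaccination, and protocol 5.2.7.1 repeats the allowance.

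The exclusion lists in protocol 12.2.3 and SAP 5.2.1 contain no COVID-19 item. Both sections close with a statement that recipients of such a vaccine are not withdrawn from the study.

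**Category 2/3 products.** For both infant sets, protocol 12.2.3 excludes without a time limit: "Subject received a protocol-prohibited medication or vaccine (identified among category 2 and 3" (with a reference to Section 6.7). It adds that "The list can be completed at the time of SAP writing and before database lock". SAP 5.2.1 adds time limits. For PPAS2: "Participant received a protocol-prohibited medication or vaccine (identified among category 2 and 3 of concomitant medications) up to V04". For PPAS3: "Participant received a protocol-prohibited medication or vaccine (identified among category 2 and 3 of concomitant medications) during the booster phase".

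SAP 5.2.1 does not say when the booster phase begins. SAP 4.3.4.2 computes its duration as "Date of latest Visit 06 - date of earliest Visit 05] + 1", and SAP 4.3.4.3 ("For the booster phase, the duration of participant participation will be computed as follows") also counts from the Visit 05 date. SAP 5.7 declares one change from the protocol, a polio threshold.

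Protocol 5.2.7.1 lists contraindications that look back from each infant dose. They include "Receipt of any vaccine (other than the study vaccine[s]) in the 4 weeks preceding the study vaccination" (2 weeks for influenza and COVID-19 vaccines) and "Long-term systemic corticosteroid therapy (prednisone or equivalent for more than 2 consecutive weeks within the past 3 months preceding the study vaccination".

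**The concern.** Immunogenicity is analyzed first on the per-protocol sets (SAP 5.2.5), so their membership should follow from the written rules.

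The main problem is that a removal recommended in one protocol section never reaches the lists that define the sets. The bullet on prohibited products does not stand in for it, because it needs a product that the protocol prohibits, and the protocol permits COVID-19 vaccine over part of the interval in which 5.2.9 recommends removal.

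The second problem is that the SAP shortens the period over which category 2/3 products exclude an infant. Depending on where the booster phase starts, the weeks before Dose 4 may be covered by neither bullet.

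What is at stake is who counts as per-protocol, and so the per-protocol percentages and geometric means at 1 month post-dose 3 (PD3) and post-dose 4 (PD4).

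**Working it through.** **1. COVID-19 vaccine: which exposures the lists reach.** The draw is due 30 to 44 days after the last dose before it (V04 is V03 + 30 [+14] days; V06 is V05 + 30 [+14] days). Counting days from that dose:

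| Timing of COVID-19 vaccine | Protocol 5.2.9 | Criterion 21 | Caught by the prohibited-product bullet? |
|---|---|---|---|
| Day 0 to 7 | Removal recommended (both situations) | Inside the 2 weeks | Arguably: other vaccines are category 2, but 5.2.9 calls the interval only desirable |
| Day 8 to 13 | Removal recommended (before the draw) | Inside the 2 weeks | Arguably, as above |
| Day 14 to the draw | Removal recommended (before the draw) | Permitted | No |

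The last row spans 30 − 14 = 16 days if the draw is on day 30, and 44 − 14 = 30 days if it is on day 44. This counts only the last dose before the draw. If Doses 1 and 2 also count for the V04 draw, the interval is longer; 5.2.9 does not say which doses count.

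The mismatch concerns infants. The toddler criterion (number 17) makes an exception for influenza vaccine only.

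**2. Category 2/3 bullet: where the pre-Dose 4 look-backs fall.** Days are counted from V03.

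- Latest in-window V04: 30 + 14 = 44.
- Earliest in-window V05: 180 − 14 = 166.
- Shortest V04 to V05 interval: 166 − 44 = 122 days.

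| Look-back before Dose 4 | Length (days) | Opens no earlier than | Days after latest V04 |
|---|---|---|---|
| Influenza or COVID-19 vaccine | 14 | 166 − 14 = 152 | 152 − 44 = 108 |
| Any other vaccine | 28 | 166 − 28 = 138 | 138 − 44 = 94 |
| Long-term corticosteroids, 3 months | about 92 (assumed) | 166 − 92 = 74 | 74 − 44 = 30 |

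With in-window visits, every look-back opens after the PPAS2 bullet has ended at V04. If the booster phase starts at V05, every look-back also lies before the PPAS3 bullet begins. PPAS3 is defined as a subset of the FAS, not of PPAS2, so nesting does not close the interval.

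**3. Size per infant.** The plan's evaluable numbers reproduce: 175 × 0.80 = 140 at PD3 and 175 × 0.70 = 122.5, stated as 122, at PD4. One infant is then 1/140 = 0.7 points at PD3 and 1/122 = 0.8 points at PD4.

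At an assumed 90% response, dropping one non-responder gives 110/121 − 110/122 = 0.75 points at PD4 and 126/139 − 126/140 = 0.65 points at PD3. The exact 95% interval for 110/122 is 83.4% to 94.8%, a half-width of about 5.7 points. Removing 7 non-responders moves the estimate by 110/115 − 110/122 = 5.49 points, so 8 of the 12 non-responders would be needed to exceed the half-width. If those removed were all responders, about 45 would be needed: 110/122 − 65/77 = 5.7 points.

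**The case against.** **On COVID-19 vaccine.** Section 5.2.9 only recommends removal and depends on a pediatric campaign taking place. The SAP repeats protocol 12.2.3, so this is a mismatch inside the protocol that the SAP inherits, not a SAP departure. All of that stands, and it is why the fix offers two routes. It does not settle the matter, because the SAP must still say whether the recommendation is applied.

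A reader might take the not-withdrawn sentence as a decision to keep these infants per-protocol. The text does not support that: 5.2.9 itself combines per-protocol removal with staying in the study. Nor do the documents support saying that every COVID-19 recipient escapes the lists, since a vaccine given within 2 weeks of a dose may be treated as a prohibited category 2 product.

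**On the category 2/3 bullet.** The time limits look like sensible matching to phase: without them, a product taken after the V04 draw could exclude an infant from the PD3 set, which it cannot have affected. The V05 start comes from formulas for computing durations, not from a rule for assigning deviations. The protocol has an end-of-phase form at V04, so time after V04 could be read as booster phase, which leaves no gap. And giving Dose 4 despite a contraindication can be seen as a deviation at V05 itself, or as administration not done as per-protocol, which is a separate PPAS3 bullet.

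These arguments have force. A reader might infer that the SAP certainly keeps infants with a contraindicated exposure before Dose 4. The documents do not go that far: the gap exists on one literal reading, and another bullet may close it. What remains is that the SAP shortened an untimed rule, did not say how the look-backs are handled, and did not declare the edit.

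**Conclusion.** The point holds as a minor one.

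- **Main part.** As written, the lists keep in PPAS2 and PPAS3 an infant given COVID-19 vaccine from day 14 to the draw, contrary to the recommendation in 5.2.9. This follows from the text alone. An earlier vaccine is only arguably caught.
- **Secondary part.** The SAP narrows the category 2/3 exclusion without declaring it. Exposures in the look-backs before Dose 4 are uncovered only if the booster phase starts at V05 and no other bullet is applied.

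The documents give no frequency for either kind of exposure; the number is probably small and could be zero. Each infant moves a per-protocol percentage by at most about 0.8 points at PD4 or 0.7 at PD3. It would be wrong to infer that a handful of reclassified infants could distort the results: on the assumed 90% response, moving a PD4 estimate by half its interval width takes 8 non-responders or about 45 responders in one group. The study is descriptive, no hypothesis is tested, and every primary and secondary immunogenicity analysis is also run on the FAS, which does not change.

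**What to change.** 1. In SAP 5.2.1, add to PPAS2 and PPAS3 an exclusion for the two 5.2.9 situations.
   - PPAS2: COVID-19 vaccine on day 0 to 7 after Dose 1, 2 or 3, or between a primary-series dose and the V04 draw, stating which doses count.
   - PPAS3: COVID-19 vaccine on day 0 to 7 after Dose 4, or between Dose 4 and the V06 draw.
   - If removal is not intended, reconcile protocol 5.2.9 with 12.2.3 instead.
2. Reword the PPAS3 category 2/3 bullet to cover the booster phase (V05 to V06) or the category 2/3 look-backs before Dose 4 in protocol 6.7 and 5.2.7.1. Name the data source: Section 6.7 starts case report book collection on each vaccination day, though medications begun earlier may be included, while the fourth diary card spans V04 to V05.
3. Declare the time limits and the added items in SAP 5.7.

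Protocol 12.2.3 allows the list to be completed in the SAP before database lock, so the first route needs SAP wording only. The cost is a possibly smaller PPAS2 and PPAS3: at an assumed 90%, removing one infant changes the width of the exact 95% interval by about 0.1 to 0.3 points (from 11.4 to 11.5 or 11.1 at PD4, and from 10.6 to 10.7 or 10.4 at PD3).
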